4.4.3. Visit Windows

Analysis data will be summarized according to the scheduled visit time period for which they were recorded in the eCRF unless otherwise specified.

4.4.4. Unscheduled Visits

Unscheduled assessments will not be slotted to a particular time point, but will be used when determining the worst-case value. All unscheduled visits will be included in listings.

4.4.5. Display of Data Summary and Analysis

Continuous variables will be summarized using descriptive statistics, including the following: sample size (n), mean, standard deviation (SD), median, first quartile (Q1), third quartile (Q3), minimum and maximum for each treatment group.

All mean, Q1, Q3 and median values will be formatted to one more decimal place than the measured value. SD values will be formatted to two more decimal places than the measured value. Minimum and maximum will be formatted to the same number of decimal places as the measured value.

Confidence intervals (CIs) will be two-sided and displayed to the same level of precision as the statistics they relate to. If an estimate or a CI is not estimable, it will be presented as 'NE'. If neither an estimate, nor its CI are estimable, it will be presented as simply 'NE', not displaying 'NE' twice.

The p-values will be two-sided and will be rounded to three decimal places. If a p-value is less than 0.001, it will be reported as '<0.001'. If a p-value is greater than 0.999, it will be reported as '>0.999'.

Categorical and ordinal data will be summarized using the counts and percentages. When count data are presented, the percent will be suppressed when the count is zero in order to draw attention to the non-zero counts. A row denoted 'Missing' will be included in count tabulations

for demographics, baseline characteristics and compliance to account for missing values. No percentages will be displayed on the ‘Missing’ rows and the percentages on the other rows will be based on the number of non-missing observations. Unless otherwise specified, the denominator for all other percentages will be the number of participants in that treatment within the specific analysis set of interest. All percentages will be rounded to one decimal place. The number and percentage of responses will be presented in the form xx (xx.x), where the percentage is in the parentheses. When the numerator is equal to the denominator, the percentage should be presented as (100) instead of (100.0).

All listings will be sorted for presentation in order of assigned treatment arm, study center number, participant number and date of procedure or event.

4.4.6. Baseline, Study Day and Duration Derivations

The baseline value of efficacy parameters is defined as the last available valid (non-missing) value up to randomization.

The baseline value of safety parameters is defined as the last available valid (non-missing) value prior to the first dose of IMP. For participants randomized and not treated, the baseline value is defined as the last available valid (non-missing) value obtained up to the date and time of randomization.

Baseline safety and pharmacodynamic results are presented in the safety and pharmacodynamic analyses.

The safety and PK analyses reference day (denoted as Day 1) for the calculation of study day of safety and PK assessments will be the date of first dose of IMP. The reference day (denoted as Day 1) for the calculation of study day of pharmacodynamic assessments will be the randomization date.

- For visit prior to the reference day, study day = assessment date – reference date.
- For visit at or after the reference day, study day = assessment date – reference date + 1.

Intervals that are presented in weeks will be transformed from days to weeks by using (without rounding) the following conversion formula:

$$\text{WEEKS} = \text{DAYS} / 7$$

Intervals that are presented in months will be transformed from days to months by using (without rounding) the following conversion formula:

$$\text{MONTHS} = \text{DAYS} / 30.4375$$

4.4.7. Change From Baseline and Percent Change From Baseline

Change from baseline is defined as: Change from baseline = Value at specific time point – Baseline value

Percent change from baseline is defined as:

$$\text{Percent change from baseline}(\%) = \frac{\text{Value at specific timepoint} - \text{Baseline value}}{\text{Baseline value}} \times 100\%$$

5. SUBJECT DISPOSITION

5.1. Disposition

The patient disposition will be summarized for the screened set by treatment group and overall using number and percentage. This section describes patient disposition for both patient study status and the patient analysis sets.

For patient study status, the number and percentage of patients in the following categories will be presented:

- Screened patients
- Screen failure patients
- Patients treated without being randomized
- Randomized patients
- Randomized but not treated patients
- Randomized and treated patients
- Patients who permanently discontinued treatment (by reason)
- Patients who have completed the study treatment period as scheduled
- Patients with premature end of study (by reason)
- Patients who completed study

For screened, screen failure, and patients treated without being randomized, percentages will be calculated using the number of screened patients as the denominator for overall only. All other categories of patients will be presented by treatment group and for overall whilst the percentages will be calculated using the number of randomized patients within each treatment group and overall, as denominator. Reasons for treatment discontinuation will be supplied in tables showing number and percentage by treatment group. A CONSORT diagram summarizing the patient disposition will also be constructed.

Listings of randomization assignment and drug actually received will be provided by participant. If applicable, patients randomized but not treated and those whose randomization code was broken will be identified and described in separate listings. Additionally, a summary of the analysis sets for screened, intent-to-treat (ITT), modified intent-to-treat (mITT), full analysis set (FAS), and PK will be provided by treatment group and overall using number and percentage.

A listing of patients excluded from analysis sets will be provided. Patients with permanent treatment discontinuation (early withdrawals) will be identified and described in separate listings.

The disposition of screened patients by country and site will be summarized for the screened analysis set by treatment group and overall using number and percentage.

5.2. Protocol Deviations

All important protocol deviations including randomization and drug-dispensing irregularities will be summarized in general and according to COVID-19 impact (ie, deviations related to COVID-19 pandemic and deviations not related to COVID-19 pandemic) for the ITT analysis set by treatment group and overall using number and percentage.

A listing of all protocol deviations will be provided. A summary table of patients with at least one important protocol deviations will be provided.

Randomization and drug-dispensing irregularities occur whenever:

1. A randomization is not in accordance with the protocol-defined randomization method, such as a) an ineligible patient is randomized, b) a patient is randomized based on an incorrect stratum, c) a patient is randomized twice, or d) in a dynamic randomization scheme the treatment assignment is, in fact, not random, due to a computer program error.

OR

2. A patient is dispensed an IMP kit not allocated by the protocol-defined randomization, such as a) a patient at any time in the study is dispensed a different treatment kit than as randomized (which may or may not contain the correct-as-randomized IMP), or b) a non-randomized patient is treated with IMP reserved for randomized patients.

Randomization and drug-dispensing irregularities will be monitored throughout the study and reviewed on an ongoing basis.

All randomization and drug-dispensing irregularities will be documented in the clinical study report. If the number of irregularities is large enough to make a tabular summary useful, the critical or major irregularities will be categorized and summarized for the ITT analysis set by treatment group and overall using number and percentage.

A listing of patients with at least one important protocol deviation related to randomization and drug-dispensing irregularities will be provided.

Randomization and drug-dispensing irregularities to be prospectively identified include but are not limited to:

Randomization and drug allocation irregularities

- Kit dispensation without IRT transaction
 - Erroneous kit dispensation
 - Kit not available
 - Randomization by error
 - Patient randomized twice
 - Forced randomization
 - Stratification error
 - Patient switched to another site
-

6. DEMOGRAPHICS AND BASELINE CHARACTERISTICS

The demographics, patient characteristics and baseline disease characteristics will be summarized using the ITT analysis set by treatment group and overall using descriptive statistics or using number and percentage. P-values on the treatment difference for the demographic and baseline characteristics data will not be calculated. In general, no specific description of the safety parameters will be provided at baseline. If relevant, the baseline values will be described along with each safety/pharmacodynamic analysis.

6.1. Demographics

The following demographics and patient characteristics will be summarized by treatment group and overall:

- Age (years),
- Age categories (<75, ≥75),
- Gender (Male, Female),
- Ethnicity (Hispanic or Latino, Not Hispanic or Latino, Not Reported),
- Race (American Indian or Alaska Native, Asian, Black or African American, Native Hawaiian or Other Pacific Islander, White, Other, Multiple),
- Baseline body weight (kg) with grouping (<70, ≥70 to <100, ≥100),
- Baseline height (cm),
- Baseline body mass index (BMI) (kg/m²) derived as: (Weight in kg)/(Height in meters)²,
- Baseline BMI categories (<25, ≥25 to <30, ≥30).

The categories presented above may be modified in case of too few subjects (≤3).

Patient demographic and baseline characteristics will also be presented in a listing.

6.2. Baseline Disease Characteristics

The following baseline disease characteristics will be summarized by treatment group and overall:

- Diagnostic criteria for apathy (DCA) by criterion: A, B, C, D (yes, no)
- Primary diagnosis (AD, FTD, VAD, or DLB), based on Dementia History
- Mini-Mental State Examination (MMSE) (<12, ≥12 to ≤26, >26)
- Dementia History (see [Section 6.5](#))
- Baseline NPI Apathy/Indifference score
- Baseline NPI-C Apathy score
- Baseline DAIR score

- Baseline AES-C score
- Baseline ADAS-Cog score
- Randomization stratum of concomitant use of SSRI/SNRI (Yes, No)
- Catechol-o-methyltransferase (COMT) status (Val/Val, Met/Val, Met/Met)

Clinical Dementia Rating (CDR) was removed as an inclusion/exclusion criterion from protocol (Amendment Version 3.0), and scores for patients with CDR scores will be listed, as well as other baseline disease characteristics.

6.3. Alcohol and Drugs Usage

Substance use, amount and frequency will be collected in the CRF at baseline and usage (current, previous, never) will be summarized by treatment group and overall. A listing will be displayed with all information collected in the CRF at baseline.

6.4. Medical History

6.4.1. General Medical History

Medical and psychiatric history includes all the relevant medical and psychiatric history during the lifetime of the patient.

Medical and psychiatric history will be coded to “preferred term (PT)” and associated primary “system organ class (SOC)” using the version of Medical Dictionary for Regulatory Activities (MedDRA) in effect at the time of database lock.

The number and percentage of participants with any medical and psychiatric history will be summarized by treatment group and overall and by each SOC and PT. SOC will be sorted in descending order of frequency based on the total of all treatment groups. A listing will be provided.

6.4.2. Dementia History

Dementia history (type and time since diagnosis) will be summarized as part of the baseline disease characteristics.

6.5. Inclusion and Exclusion Criteria

Inclusion and exclusion criteria will be presented for the screened analysis set for each treatment group and screen failure subjects using number and percentage. A listing of excluded patients with the met/unmet inclusion/exclusion criteria will be provided.

7. TREATMENTS AND MEDICATIONS

7.1. Prior, Concomitant and Post-Treatment Medications

The prior and concomitant medications will be presented for the ITT analysis set for each treatment group and overall using number and percentage. No statistical test for the between-group difference will be performed.

All medications will be coded using the World Health Organization-Drug Dictionary (WHO-DD) using the version in effect at the time of database lock.

Medications will be summarized by treatment group according to the WHO-DD, considering the first digit of the anatomic category (ATC) class (anatomic category) and the first 3 digits of the ATC class (therapeutic category). All ATC codes corresponding to a medication will be summarized, and patients will be counted once in each ATC category (anatomic or therapeutic) linked to the medication. Therefore, patients may be counted several times for the same medication.

The summaries for prior, concomitant and post-treatment medications will be sorted by decreasing frequency of ATC followed by all other therapeutic classes based on the total incidence across treatment groups. In case of equal frequency regarding ATCs, alphabetical order will be used.

For the purpose of inclusion in prior and/or concomitant medication tables, incomplete medication start and stop dates will be imputed as described in [Section 17.2.2](#). Prior, concomitant, and post-treatment medications, their start/end dates and frequencies will be presented in a listing.

7.1.1. Prior Medications

Prior medications are those the patient began prior to first IMP intake. Prior medications can be discontinued before first treatment administration or can be ongoing during the treatment phase.

7.1.2. Concomitant Medications

Concomitant medications are any treatments received by the patient concomitantly to the IMP, starting from the 1st administration of IMP to the date of last administration. A given medication can be classified both as a prior medication and as a concomitant medication.

7.1.3. Post-Treatment Medications

Post-treatment medications are those the patient took (continued or initiated) in the period running from the day after the last administration of IMP up to the end of the study.

7.2. Study Treatments

7.2.1. Extent of Exposure

The extent of IMP exposure will be assessed by the duration of IMP exposure.

Duration of IMP exposure is defined as (last IMP administration dose date – first IMP administration dose date + 1 day), regardless of unplanned intermittent discontinuations. Last IMP administration date is defined as the last available administration date in the “Exposure” form. The reason for early treatment discontinuation will also be based on this last available Exposure form.

Duration of IMP exposure (in weeks) will be summarized descriptively as a quantitative variable (number, mean, SD, median, Q1, Q3, minimum and maximum). In addition, duration of IMP exposure will also be summarized categorically by numbers and percentages for each of the following categories and cumulatively according to these categories:

- >0 and ≤3 weeks
- >3 and ≤6 weeks
- >6 and ≤12 weeks
- >12 weeks

The extent of IMP exposure will be assessed and summarized by actual treatment group and overall for the FAS.

7.2.2. Treatment Compliance and Modifications

Percentage of compliance will here only be calculated and considered from the day after last up-titration, ie, per schedule, from Day 23 on. In this setting, percentage of compliance for a patient will be defined as the number of tablets the patient has taken (# of dispensed - # of returned - 1) divided by the total number of tablets that the patient was planned to take during the last treatment period (from Day 23 [the day after Visit 4] on to the last date of IMP administration). That is, for patients taking IMP till at least Day 23, we define the following:

$$\text{Percentage of compliance (\%)} = \frac{[(\# \text{ of dispensed} - \# \text{ of returned} - 1)]}{(\text{Final Dosing Stop Date} - (\text{Final Dosing Start Date} + 1))} \times 100\%$$

Percentage of compliance will be summarized descriptively as a quantitative variable (number, mean, SD, median, Q1, Q3, minimum and maximum). In addition, the percentage of compliance will be presented by the specific ranges for each treatment group:

- <80%
- ≥80% to <120%
- ≥120%

Dose modification of IMP for an individual patient is not allowed and therefore no summary of dose modifications will be provided. Down titrations allowed per protocol will be summarized.

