On Day 22 (Visit 4), all subjects will take the Step 5 dose of IMP at the clinic. Subjects will be monitored for tolerability while undergoing concurrent assessments; after completion of all visit procedures, the investigator will assess whether the participant will continue with the new dose. Subjects who are unable to tolerate the dose at Step 5 may go back to the dose at Step 4 and continue on that dose for the remainder of the trial. Subjects who are able to tolerate the Step 5 dose will continue on this dose for the remainder of the trial and no further dosing adjustments are allowed.

[figure not shown]
Lack of tolerability should be of sufficient severity that it results in significant dysfunction or distress to the subject (eg, Common Terminology Criteria for Adverse Events [CTCAE] Grade 2/3). The medical monitor should be contacted in any instance

where the investigator is uncertain whether the subject is able to tolerate the stepwise dose increase.

No deviations in the dosing schedule, other than those noted above, are allowed.

The titration scheme, including the dosing decision time points, is presented in [Figure 2](#).

Figure 2 Dosing Schematic

Abbreviations: PBO = placebo.

Note: If “Yes” then continue with new dose; if “No” then stay at previous dose.

Assessments will be conducted at the Week 1, 3, 6, and 12 visits. Subjects will be instructed to take their dose of IMP at the clinic on days when visits occur. Blood samples for PK analysis will be collected at the Week 1, 3, 6, and 12 visits.

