4.2. Randomization, Stratification, and Blinding

During the entire trial, treatment will be double-blind. Treatment assignments will be based on a computer-generated randomization code provided by Cerevel or designee. Access to the treatment codes will be restricted to personnel charged with generating and maintaining randomization files, packaging IMP, operating the Interactive Response Technology (IRT), and reporting Serious Adverse Events (SAEs) to regulatory agencies. Once a randomization number has been assigned, it must not be reassigned. A participant cannot be randomized more than once in the study.

Randomization will be stratified according to 2 distinct strata:

- Subjects currently using SSRIs or SNRIs during the trial
- Subjects not using SSRIs or SNRIs

The CVL-871 and placebo tablets will be identical in appearance and will be packaged in identically appearing bottles. All subjects will take a single tablet, either CVL-871 or placebo, once daily throughout the Treatment Period. Tablets will be packaged to allow dosage adjustments to be made without breaking the trial blind.

Documentation of breaking the blind should be recorded on the subject's medical record with reason for breaking the blind, the date and time the blind was broken, and the names of the personnel involved. Once the blind is broken for a subject, reinitiation of treatment with IMP cannot occur for that subject.

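### The printed compliance denominator in SAP 7.2.2 is one day short of its verbal definition: full adherence to Day 84 gives 101.6%, and a Day 23 stop divides by zero.

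*SAP*

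**What the plan says.** SAP 7.2.2 limits compliance to the last dosing stage: "Percentage of compliance will here only be calculated and considered from the day after last up-titration, ie, per schedule, from Day 23 on". The numerator is "the number of tablets the patient has taken (# of dispensed - # of returned - 1"). The denominator in words is the "total number of tablets that the patient was planned to take during the last treatment period (from Day 23 [the day after Visit 4"], running to the last date on which IMP was taken. The formula is said to apply generally: "for patients taking IMP till at least Day 23, we define the following". The displayed denominator is then Final Dosing Stop Date - (Final Dosing Start Date + 1). Neither date is defined in the section. Results are summarised as a continuous variable and in three ranges: below 80%, 80% to below 120%, and 120% or more.

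Three other places bear on the count:

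- SAP 4.2: "All subjects will take a single tablet, either CVL-871 or placebo, once daily".
- SAP 3.4, Table 2: Step 5 runs from Day 22 to Day 84, with 63 expected days.
- SAP 7.2.1: exposure is "last IMP administration dose date – first IMP administration dose date + 1 day", which is an inclusive count.

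**The concern.** The words and the displayed formula should give the same number of planned tablets, but they differ by one. Counting tablets from one day to another, both included, needs last - first + 1. SAP 7.2.1 has that +1; the compliance denominator does not. Its only +1 moves the start from Day 22 to Day 23, which is a different adjustment. The numerator already removes one tablet to match a Day 23 start, so it follows the words and not the printed denominator.

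If programmed as printed, reported compliance is too high wherever it can be computed, and one missed tablet always shows as 100%. Fully adherent subjects who stop soon after the last up-titration fall in a range that reads as taking too many tablets. A Day 23 stop has no value at all. Enrollment closed before the planned sample size was reached, so a single extreme value would weigh more in the mean, the maximum and the range percentages.

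**Working it through.** **Inputs**

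- Step 5 starts on Day 22 at Visit 4 and ends on Day 84 (SAP Table 2; Protocol 4.1.2).
- One tablet a day (SAP 4.2).
- Assumed, because undefined in 7.2.2: Start = Day 22 and Stop = last IMP date, Day L.
- Also inferred: the numerator's -1 removes the Day 22 tablet.

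**Reproducing the SAP's own day counts.** With last - first + 1, Table 2 is matched exactly:

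- Days 1-3: 3 - 1 + 1 = 3
- Days 4-7: 7 - 4 + 1 = 4
- Days 8-16: 16 - 8 + 1 = 9
- Days 17-21: 21 - 17 + 1 = 5
- Days 22-84: 84 - 22 + 1 = 63

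**Denominators**

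- In words: N = L - 23 + 1 = L - 22. For L = 84, N = 62.
- As printed: L - (22 + 1) = L - 23 = N - 1. For L = 84, this is 61.

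**Numerator at full adherence:** (L - 22 + 1) - 1 = N. For L = 84, 63 - 1 = 62.

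Full adherence is therefore reported as N/(N - 1):

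| Last dose day | Planned N | Printed result | Value |
|---|---|---|---|
| 23 | 1 | 1/0 | undefined |
| 24 | 2 | 2/1 | 200% |
| 25 | 3 | 3/2 | 150% |
| 26 | 4 | 4/3 | 133.3% |
| 27 | 5 | 5/4 | 125% |
| 28 | 6 | 6/5 | 120% |
| 29 | 7 | 7/6 | 116.7% |
| 43 | 21 | 21/20 | 105.0% |
| 57 | 35 | 35/34 | 102.9% |
| 84 | 62 | 62/61 | 101.6% |

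N/(N - 1) is at least 1.2 only for N of 6 or less, so Day 28 is the last stop at which full adherence reaches the top range.

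**One missed tablet:** (N - 1)/(N - 1) = 100% for every N of 2 or more. At Day 84 the correct value is 61/62 = 98.4%.

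**The 80% cut.** A tablet count k changes range if 0.8(N - 1) <= k < 0.8N. For N = 62 this is 48.8 <= k < 49.6, so k = 49: correct 49/62 = 79.0%, printed 49/61 = 80.3%. Over N = 2 to 62 there is exactly one such count unless N is a multiple of 5, when there is none. That is 61 - 12 = 49 of the 61 durations.

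**The 120% cut.** Unreturned tablets count as taken, so counts above plan can occur. At N = 62, 1.2 x 61 = 73.2 and 1.2 x 62 = 74.4, so k = 74 changes range: 74/62 = 119.4% becomes 74/61 = 121.3%.

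**Other readings**

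- Start = Day 23: 62/(84 - 24) = 62/60 = 103.3%. The gap widens.
- Last dose on Day 85 (Visit 6): 63/62 = 101.6%. Nothing changes after rounding.

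**The case against.** The two dates may be case report form fields whose definitions are not visible. If the recorded stop date were the day after the last tablet, say Day 85 for a last tablet on Day 84, the printed formula would give 62/62. The displayed equation was also read from PDF, and a different bracketing, (Stop - Start) + 1 with Start = Day 23, would give 100%.

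Neither reading is supported by the text. The verbal definition ends the period at the last IMP date itself, and the nested bracket fits the day-after wording, so a misreading is possible but not shown.

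Some qualifications do stand:

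- The day numbers assume that Visit 4 falls on Day 22. The schedule allows visit windows, so they shift with the actual start date, and durations beyond 62 planned tablets are possible. The 49 of 61 count holds for the nominal schedule only.
- The undefined and 120%-or-more results at full adherence need a stop within six days of Day 22. The documents do not say how many subjects did so.
- A zero denominator would surface in programming. The inflation of about 1.6 percentage points at Day 84 might not, because double programming from the same formula reproduces it.

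**Conclusion.** The formula is wrong as printed. It contradicts the verbal definition in the same section by one day and departs from the inclusive count in SAP 7.2.1 and Table 2. This rests on Start = Day 22, Stop = last IMP date and one tablet a day; no reading that the text supports removes the discrepancy.

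The severity is minor. The usual error, for subjects dosed to Day 84, is 101.6% in place of 100%, with one below-plan count (49 tablets) moved across the 80% cut. The large errors are limited to stops soon after the last up-titration. No analysis set, endpoint or model uses this percentage, and the protocol's 80% compliance rule (6.4) concerns overall compliance and is applied separately.

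**What to change.** In SAP 7.2.2:

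1. Define Final Dosing Start Date as the date of the Step 5 dose at Visit 4 (Day 22 per schedule), and say that the numerator's -1 removes that tablet.
2. Define Final Dosing Stop Date as the last IMP administration date.
3. Change the denominator to Stop - Start, which equals Stop - (Start + 1) + 1. A Day 84 stop then gives 62/(84 - 22) = 62/62 = 100%, and a Day 23 stop gives 1/(23 - 22) = 1/1 = 100%.
4. Protocol 4.1.2 provides that "Subjects who are unable to tolerate the dose at Step 5 may go back to the dose at Step 4". State that compliance for these subjects is computed on the same Day 23 basis, so that numerator and denominator cover the same days. This is a related gap in the definitions and not part of the arithmetic error.

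The cost is two definitions, one formula term, one clarifying sentence and one line of code. No new data are needed and no treatment rule changes.
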